1. INTRODUCTION

1.1 SICKLE CELL DISEASE

Sickle cell disease (SCD), a group of genetic blood disorders affecting hemoglobin.⁽²⁾ The inherited mutation results in a substitution of the amino acid valine for glutamic acid in the 6th position of the beta globin chain causing the formation of hemoglobin S (HbS).⁽³⁾ When deoxygenated, this hemoglobin polymerizes into rigid chains that deform red blood cells (RBCs) into the characteristic sickle shape. These less-flexible, sickled RBCs cause inefficient blood flow to organs and tissues and are more susceptible to hemolysis, with an average lifespan of approximately 20 days versus 120 days for normal RBCs.⁽⁴⁾ Upon hemolysis, hemoglobin released into the plasma scavenges nitric oxide (NO), which reduces NO bioavailability and in turn leads to vasoconstriction, endothelial dysfunction, and systemic inflammation.^(5, 6) The combined effects of vasoconstriction, inflammation, and leukocyte adhesion to the endothelium are believed to contribute to many symptoms of SCD, including painful vaso-occlusive crises and chronic pain. SCD is the most common genetic hematological disorder worldwide, with millions affected, including approximately 100,000 Americans.⁽²⁾ Globally, it is estimated that more than 300,000 children are born with the disease each year.⁽⁷⁻⁹⁾

Nonclinical safety data support investigation of IW-1701 in the age range proposed for this study. The progression of SCD varies, but in general, during the first years of life, patients are at risk for complications such as: acute chest syndrome precipitated by infection, infarction, embolism, and pulmonary sequestration; pleuritic pain due to avascular necrosis of ribs or sternum; strokes (median age of onset, 6 years with recurrent strokes in 50%–70%); hypersplenism leading to splenectomy and/or chronic transfusion; and aplastic crisis.⁽¹⁰⁾ In later childhood and early adolescence, patients may experience nocturnal enuresis, bone pain crises, avascular necrosis of the femoral head, chronic leg ulcerations, delayed growth and puberty and, in boys, priapism. In adulthood, the risk for hemorrhagic stroke peaks and the risk for acute chest syndrome continues. In addition, increased pulmonary fibrosis and pulmonary hypertension stress cardiac function, and progressive glomerular fibrosis and associated decrease in glomerular filtration rate often lead to renal failure.⁽¹⁰⁾ Because patients are affected by this congenital disease starting at birth, they may benefit from earlier therapeutic intervention.

Hydroxyurea (HU) is approved by the Food and Drug Administration (FDA) and is indicated to reduce the frequency of painful crises and the need for blood transfusions.(11, 12) Warnings for the use of HU include myelosuppression, secondary malignancies, embryo-fetal toxicity, cutaneous vasculitic toxicities, and macrocytes, and patients on HU require periodic laboratory tests to monitor for cytopenias. The side effects as well as issues with patient compliance with HU therapy and/or lab monitoring have contributed to low overall utilization rates.(13)

Hydroxyurea (SIKLOS) was approved by the FDA in 2017 for the treatment of pediatric patients as young as 2 years of age.(14)

L-glutamine (ENDARI) was approved by the FDA in 2017 (15) and is indicated to reduce the acute complications of SCD in adults and in children older than 5 years. Both ENDARI and SIKLOS are the first SCD medicines to be approved for pediatric patients in the US. ENDARI is the first new treatment for adults with SCD in nearly 2 decades.

There remains considerable unmet medical need in SCD, not only for treatments that prevent painful crises and other acute complications, but also for treatments that address the daily symptoms of the disease, including chronic pain.

1.2 RATIONALE FOR USE OF AN SGC STIMULATOR IN SCD

NO is the primary mediator of vasodilation. Endothelial-derived NO activates the signaling enzyme, soluble guanylate cyclase (sGC), to convert guanosine triphosphate to cyclic guanosine-3',-5'-monophosphate (cGMP). In turn, cGMP stimulates protein kinases, which decrease intracellular calcium levels and relax the vascular smooth muscle. The cGMP is then degraded by phosphodiesterase (PDE) enzymes.(16) The NO-sGC-cGMP pathway is the main mechanism by which NO regulates vasodilation. In addition to regulating vascular tone, NO reduces smooth muscle proliferation and produces anti-inflammatory effects by decreasing cytokine-induced expression of adhesion molecules and decreasing the production of proinflammatory cytokines.(17) Because NO bioavailability is reduced in SCD patients, smooth muscle sGC and cGMP activity are also reduced and, consequently, vascular relaxation and vasodilation are inhibited and blood flow is reduced. Therefore, the NO-sGC-cGMP pathway offers a potential therapeutic target for increasing cGMP levels in SCD. Indeed, in mouse models of SCD, PDE9 inhibitors, which block the degradation of cGMP, have been shown to reduce leukocyte

adhesion, vaso-occlusion, and RBC sickling, and to improve survival.(18-22) sGC stimulators, which act directly on sGC to increase cGMP production, may offer another way to modulate the NO-sGC-cGMP pathway to compensate for reduced NO levels in patients with SCD.

1.3 IW-1701 BACKGROUND

The Sponsor is developing olinciguat (IW-1701), an orally administered stimulator of sGC, for the treatment of disorders that may be modulated by the NO-sGC-cGMP signaling pathway.

For a description of the properties of IW-1701 and the results of the nonclinical and clinical studies completed thus far, please refer to the most recent Investigator's Brochure (IB).

1.3.1 Nonclinical Data Supporting the Investigation of IW-1701 as a Potential Therapy for SCD

For a summary of the results of the nonclinical studies, please refer to the most recent IB.

2. STUDY OBJECTIVES

Primary

- To assess the safety and tolerability of oral, once-daily (QD) IW-1701 when administered for approximately 12 weeks to patients aged 16 to 70 years with SCD

Exploratory

- To evaluate the effect of oral, once-daily IW-1701 on symptoms of SCD, health-related quality of life, and biomarkers when administered for approximately 12 weeks to patients aged 16 to 70 years with SCD
- To evaluate the pharmacokinetics (PK) of oral, once-daily IW-1701 when administered for approximately 12 weeks to patients aged 16 to 70 years with SCD

3. INVESTIGATIONAL PLAN

3.1 OVERALL STUDY DESIGN AND PLAN

Note: *Patients randomized prior to Amendment 4 will continue to be treated according to Amendment 3 for the duration of their study participation. Please see Amendment 3 for details.*

[figure not shown]
Procedural changes made in association with Amendment 4 will apply only to new patients randomized under that amendment and beyond.

This multicenter, randomized, double-blind, placebo-controlled, parallel-group study with a 2-week single-blind run-in will evaluate oral IW-1701 administered QD for approximately 12 weeks compared with placebo.

The overall study will randomize approximately 88 patients with SCD (~40 patients randomized under Amendment 3 or earlier; ~48 under Amendment 4 and beyond). The patients will be between 16 to 70 years of age and, if taking HU, will be on a stable regimen (refer to Section 3.4.1 for a description of the study population; see [Eligibility Criteria](#) for full details). After a 2-week, single-blind, placebo Run-in Period, eligible patients will be stratified by HU use (yes or no) and randomly assigned in a 3:1 ratio to receive 18 mg IW-1701 QD or placebo (see [Table 2](#)).

Each patient will progress through 3 study periods: a Screening Period that will include a single-blind placebo Run-in Period, a double-blind Treatment Period, and a Follow-up Period ([Figure 1](#)).

Figure 1. Study Schematic for Amendment 4 Onward

PBO=placebo; Wk=week

Screening Period: The Screening Period will begin with the signature of the informed consent form (ICF) at the Screening Visit and may last up to 43 days. At the Screening Visit, patients will undergo preliminary procedures to determine their initial eligibility. The Screening Period will include the Run-in dosing period.

- Run-in Period:** The single-blind Run-in will begin at least 3 days after the Screening Visit and is defined as the 14 to 17 days before the first dose of double-blind study drug on Day 1. At the Run-in Visit, eligible patients will take their first single-blind (placebo) dose in the clinic, will undergo safety and pharmacodynamic (PD) assessments, and will complete patient-reported outcome (PRO) questionnaires in an eDiary (a handheld personal electronic device) that will be issued for their use. They will continue to take once-daily single-blind placebo at home and will record daily and weekly assessments in their eDiary throughout this period. Patients will be required to complete at least 10 days of daily assessments during the final 14 days of the Run-in Period to remain eligible for randomization into the Treatment Period.

Treatment Period: The double-blind Treatment Period will begin on Day 1 at Randomization (there is no Day 0) and will end after the End-of-Treatment (EOT) Visit on Day 85 (-7/+4).

Eligible patients will take their first dose of double-blind study drug in the clinic on Day 1 and will undergo safety, PRO, PK, and PD assessments at prespecified times according to the [Schedule of Events](#). Patients must remain in the clinic at least 6 hours postdose and thereafter will be allowed to leave at the Investigator's discretion. Starting on Day 2, patients will take their daily double-blind study drug dose at home, per Section [3.5.4.1](#). Also on Day 2, preferably in the afternoon, patients will receive a phone call for adverse event (AE) and concomitant medication and procedure(s) assessment. Throughout the Treatment Period, patients will continue to record daily assessments in their eDiary.

At their Week 1 (Day 8 [± 1]) and Week 4 (Day 29 [± 3]) visits, respectively, patients who meet the uptitration criteria (see Section [3.5.4.2](#)) will begin taking the applicable higher dose. At these visits, patients must again stay in the clinic at least 6 hours postdose to undergo safety, PRO, PK, and PD assessments at prespecified times according to the [Schedule of Events](#) and thereafter will be allowed to leave at the Investigator's discretion. On the day after these 3 visits, preferably in the afternoon, patients will receive a phone call for assessment of AEs and concomitant medication(s) and procedure(s).

During Week 2, Week 3, Week 4, Week 6, and Week 10, patients will receive a phone call for AE and concomitant medication and procedure(s) assessments.

At Week 12 (EOT Visit), patients will return to the clinic for safety, PRO, PK, and PD assessments and will return their eDiary and any unused study drug.

Follow-up Period: The Follow-up Period will begin immediately after the EOT Visit and will last for 28 (-3/+7) days. On Day 113 (-3/+7), patients will return to the clinic for the Follow-up Visit and final safety, PRO, PK, and PD assessments.

The study schematic ([Figure 1](#)) shows all study visits and calls. For a detailed schedule of all study visits and assessments, refer to the [Schedule of Events](#).

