17. Patient will not be able to adhere to the trial assessment schedule, or, in the clinical judgement of the Investigator, the patient is otherwise not suitable for the trial.

Note: Screening Visit assessments may take place over more than 1 day. Patients may be rescreened per Investigator judgement after consultation with the Medical Monitor. Laboratory assessments may be repeated if an error is suspected. In certain circumstances local laboratory values may be acceptable.

SCHEDULE OF EVENTS

Study Period		Screening		Treatment								F/U	
Contact Type	Visit	Visit	Visit	Call	Visit	Calls	Visit	Calls		Visit	Call	Visit	Visit
Visit Name	Screening	Run-in ^a	Random- ization	-	Week 1	-	Week 4	-	-	Week 8	-	Week 12/EOT	F/U/ EOS
Day (D)→ Procedure ↓	Day -43 to -15	Day -17 to -14	Day 1	Day 2	Day 8 ±1	Wk1 V+1D, D15±2, D22±2	Day 29 ±3	Wk4 V +1D	D43 ±2	Day 57 ±7	D71 ±2	Day 85 -7/+4	Day 113 -3/+7
ICF signed	X												
I/E confirmation	X	predose	predose										
Demographics	X												
Medical/SCD history	X												
Prior & concomitant meds & procedures	X	X	X	X	X	X	X	X	X	X	X	X	X
Physical exam ^b	X	predose	predose		predose		predose			predose		predose	X
Weight & height	W, H	W	W		W		W			W		W	W
12-lead ECG ^c	X		predose pd: 4h (±15m)		predose pd: 4h (±15m)								X
AE evaluation	X	X	X	X	X	X	X	X	X	X	X	X	X
Drug screen ^d	X												
Pregnancy test ^e	X	predose	predose		predose		predose			predose		predose	X
Urinalysis sample	X		predose		predose		predose			predose		predose	X
Oral temperature & RR	X		predose pd: 1h (±15m)		predose		predose			predose		predose	X
O ₂ saturation	X	predose	predose		predose		predose			predose		predose	X
Seated BP, pulse ^f	X		pd: 6h (±15m)		predose pd: 6h (±15m)								
Seated-to-standing BP/pulse ^g	X	X	predose pd: 1,3,6 (±15m)		predose pd: 1,3,6 (±15m)		predose pd: 1h (±15m)			predose pd: 1h (±15m)		predose pd: 1h (±15m)	X

Study Period		Screening		Treatment								F/U	
Contact Type	Visit	Visit	Visit	Call	Visit	Calls	Visit	Calls		Visit	Call	Visit	Visit
Visit Name	Screening	Run-in ^a	Randomization	-	Week 1	-	Week 4	-	-	Week 8	-	Week 12/EOT	F/U/ EOS
Day (D)→ Procedure ↓	Day -43 to -15	Day -17 to -14	Day 1	Day 2	Day 8 ±1	Wk1 V+1D, D15±2, D22±2	Day 29 ±3	Wk4 V +1D	D43 ±2	Day 57 ±7	D71 ±2	Day 85 -7/+4	Day 113 -3/+7
Clinical laboratory blood samples	X		predose		predose		predose			predose		predose	X
Genotyping blood sample (w/patient consent)			predose										

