- c. Patient must be supine for ≥5 m before the ECG recording. If QTc result is outside of normal range, perform in triplicate and calculate the average. If ECG result is clinically abnormal, repeat. If repeated ECG is also clinically abnormal, site should follow standard institutional procedures until resolved. If concerns remain, issue should be escalated to Medical Monitor.
- d. Urine screen for amphetamines, barbiturates, benzodiazepines, cocaine, opiates, phencyclidine, and propoxyphene.
- e. For women of reproductive potential, a negative pregnancy test by urine dipstick must be documented at all study visits; negative results must be confirmed before each in-clinic dosing. If urine test is positive, see Section 3.8.7.2. All patients should be reminded of birth control requirements.
- f. Seated BP at the Screening Visit, 6 hours postdose at the Randomization Visit, and at predose and 6 hours postdose at the Week 1 Visit will be the average of 3 measurements obtained at 2-m intervals after patient has been sitting quietly for ≥5 m. Other BP and all pulse measurements may be single measurements obtained after the patient has been sitting quietly for ≥5 m.
- g. *Orthostatic measurements:* Patient must sit quietly for approximately ≥5 m before seated BP and pulse measurements are taken, and then assume standing position for 2 m (±1 m) before standing BP and pulse measurements are taken. Vital signs (including BP) must be measured before blood sampling when applicable.
- h. Not collected at sites located in Lebanon
- i. Starting with the Run-in Visit and throughout the Treatment Period, patients will be instructed to bring all study drug bottles to each clinic visit for confirmation of at-home dosing compliance via tablet count. Study drug will be resupplied as applicable.
- j. Study drug will be administered in the clinic on study visit days after predose assessments. Patients should take study drug 1 hour before or 2 hours after food, with water, and may swallow 2 tablets together, when applicable. Study drug may be taken with concomitant medications. Coffee or juice may be allowed if the patient feels faint. During the Treatment Period, dose levels will be titrated as indicated in Table 2 for patients meeting criteria in Section 3.5.4.2. See Section 3.5.4.3 for dose adjustment instructions. Instructions for temporary dosing interruptions are in Section 3.5.4.4.

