3.5.4.2 Uptitration (Week 1 and Week 4 Visits) during the Treatment Period

At the Week 1 (Day 8 ±1) Visit during the Treatment Period, patients will begin taking the uptitrated doses as noted in [Table 2](#) in the clinic *unless*: their seated systolic BP is <90 mmHg, their standing heart rate is >20 bpm greater than baseline, or they have unresolved AEs that, in the Investigator's opinion, should preclude uptitration.

- If a patient *does* uptitrate at the Week 1 Visit to 12 mg QD, the patient will be considered for uptitration to 18 mg QD at the Week 4 Visit (Day 29 ±3) based on the criteria listed above.
- If a patient *does not* uptitrate at the Week 1 Visit to 12 mg QD, the patient will remain on 6 mg QD and will be re-assessed at Week 4 for titration to 12 mg QD. If he/she is then uptitrated to 12 mg QD at Week 4, he/she will remain on 12 mg QD for the remainder of the study. If the patient does not meet criteria for uptitration to 12 mg QD at Week 4, he/she will remain at the 6-mg dose for the remainder of the study.

On the day after any uptitration or dose adjustment, preferably in the afternoon, the patient will receive a phone call for AE and concomitant medication assessments. Additional phone calls will be conducted per the [Schedule of Events](#).

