3.5.4.3 Dose Adjustments

It is recommended that the patient is evaluated in the clinic prior to any dose adjustment. According to his/her medical judgement, an Investigator may reduce a patient's dose as outlined below. Adjustments should be made, if possible, in consultation with the Medical Monitor.

- Patients who do not tolerate the initial 6-mg QD dose during Week 1 of the Treatment Period should be reduced to a 3-mg QD dose (ie, reduction by 1 tablet), with escalation to 6 mg QD considered at the Week 4 visit if they meet uptitration criteria (Section 3.5.4.2). Subsequent titration to 12 mg or higher will not be permitted for those patients.
- Patients who do not tolerate an uptitration to 12 or 18 mg QD should be reduced to their prior tolerated dose level (ie, 6 or 12 mg QD, respectively). Subsequent titration to a higher dose will not be permitted for those patients.
- If a patient develops any of the following **study drug-related TEAEs**, his/her dose will be reduced to his/her prior tolerated dose (or to 3 mg QD if receiving the initial 6 mg QD dose) and will not be retitrated to a higher dose:
 - 1 episode of Grade 3 vomiting (assessed per CTCAE v4.03) lasting >48 hours and not responsive to antiemetic therapy
 - 1 episode of Grade ≥3 syncope
 - 2 episodes of Grade 2 presyncope without orthostatic hypotension

On the day after any dose adjustment or uptitration, preferably in the afternoon, the patient will receive a phone call for AE and concomitant medication assessments. Additional phone calls will be conducted per the [Schedule of Events](#).

As noted above, with the exception of the lead-in dose during the first week, once a patient down-titrates, titration to a higher dose will not be permitted.

Investigators should notify the Medical Monitor of all decisions to reduce dose or to discontinue dosing on a per-patient basis.

See Section [3.4.2](#) for criteria triggering removal of individual patients from study drug dosing.

Note: Patients taking HU should be monitored for hematologic toxicities per the current prescribing information.

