3.8.6.2 Blood Pressure, Pulse, and Oxygen Saturation

Seated BP at the Screening Visit, at 6 hours postdose at the Randomization Visit (last BP of the visit), and at predose and 6 hours postdose at the Week 1 Visit will be the average of 3 measurements obtained with an appropriately sized cuff at 2-minute intervals after the patient has been sitting quietly for at least 5 minutes. Other seated BP measurements and all pulse measurements may be single measurements obtained after the patient has been sitting quietly for at least 5 minutes.

For seated-to-standing BP and pulse measurements, patients should sit quietly for at least 5 minutes before seated measurements are taken, then assume a standing position for 2 minutes (± 1 m) before standing measurements are taken. Values from these measurements will be used for calculation of orthostatic BP and pulse.

Oxygen saturation measurements should be taken by pulse oximeter on room air.

NOTE: If oxygen saturation declines below 85% or if decreasing oxygen saturation (decreasing values across 2 sequential visits), the patient should be assessed (eg, cardiovascular exam, chest x-ray, as indicated) for pulmonary edema or other causes of decreased oxygen saturation.

When applicable, BP, pulse, and oxygen saturation measurements should be taken before blood draws.

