### **3.8. Study Procedures and Flowchart**

The study schedule from screening through follow-up under Protocol Amendment 3 is presented in [Table 5a](#). (See respective study protocol for minor differences in the Schedule of Events for the original protocol through Amendment 2.) The study schedule under Protocol Amendments 4/5 is show in [Table 5b](#).

This document is confidential.

Table 5a Schedule of Events (Amendment 3)

Study Period →	Screening	Run-in	Treatment										F/U
Contact Type →	Visit	Visit	Visit	Call	Visit	Calls	Visit	Call	Visit	Call	Visit	Visit	Visit
Visit Name →	Screening	Run-in*	Randomization	-	Week 1	-	Week 4	-	Week 8	-	Week 12/ EOT		F/U
Day (D) → Procedure ↓	Day -43 to -15	Day -17 to -14	Day 1	Day 2	Day 8 ±1	Wk1 V+1D, D15±1, D22±1	Day 29 ±3	D43 ±1	Day 57 ±7	D71 ±1	Day 85 -7/+4	Day 113 -3/+7	
ICF signed	X												
I/E confirmation	X	predose	predose										
Demographics	X												
Medical history	X												
Prior & concomitant meds & procedures	X	X	X	X	X	X	X	X	X	X	X	X	
Physical exam (a)	X	predose	predose		predose		predose		predose		predose		X
Weight & height	W, H	W	W		W		W		W		W		W
12-lead ECG (b)	X		predose pd: 4h (±15m)		predose pd: 4h (±15m)								X
AE evaluation	X	X	X	X	X	X	X	X	X	X	X	X	
Drug screen (c)	X												
Pregnancy test (d)	X	predose	predose		predose		predose		predose		predose		X
Urinalysis sample	X		predose		predose		predose		predose		predose		X
Oral temperature and RR	X		predose pd: 1h (±15m)		predose		predose		predose		predose		X
O 2 saturation	X	predose	predose		predose		predose		predose		predose		X
Seated BP, pulse (e)	X		pd: 6h (±15m)		predose pd: 6h (±15m)								
Seated-to-standing BP/pulse (f)	X	X	predose pd: 1,3,6 (±15m)		predose pd: 1,3,6 (±15m)		predose pd: 1h (±15m)		predose pd: 1h (±15m)		predose pd: 1h (±15m)		X

This document is confidential.

Study Period →	Screening	Run-in	Treatment										F/U
Contact Type →	Visit	Visit	Visit	Call	Visit	Calls	Visit	Call	Visit	Call	Visit	Visit	Visit
Visit Name →	Screening	Run-in*	Randomization	-	Week 1	-	Week 4	-	Week 8	-	Week 12/ EOT	F/U	
Day (D) Procedure ↓	Day -43 to -15	Day -17 to -14	Day 1	Day 2	Day 8 ±1	Wk1 V+1D, D15±1, D22±1	Day 29 ±3	D43 ±1	Day 57 ±7	D71 ±1	Day 85 -7/+4	Day 113 -3/+7	
Clinical laboratory blood samples	X		predose		predose		predose		predose		predose	X	
Genotyping blood sample (w/consent)			predose										

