## 5. General Aspects for Statistical Analysis

### 5.1. General Methods

All applicable data will be summarized by randomized treatment arm, unless specified otherwise. For summary tables, unless otherwise noted, participants who were randomized to placebo will be summarized as:

- 1) PBO1: participants who were randomized to placebo under Protocol Amendment 3 or earlier,
- 2) PBO2: participants who were randomized to placebo under Protocol Amendment 4 or later, and
- 3) Overall: participants who were randomized to placebo under any version of the protocol.

The participants who were randomized to olinciguat dosing regimens will be summarized as:

- 1) 2 mg: participants who were randomized to 2 mg olinciguat dosing regimen under Protocol Amendment 3 or earlier,
- 2) 4 mg: participants who were randomized to 4 mg olinciguat dosing regimen under Protocol Amendment 3 or earlier,
- 3) 6 mg: participants who were randomized to 6 mg olinciguat dosing regimen under Protocol Amendment 3 or earlier, and
- 4) 18 mg: participants who were randomized to 18 mg olinciguat dosing regimen under Protocol Amendment 4 or later

For safety analysis, the data will be summarized by treatment arm actually received.

In addition, data will be summarized by scheduled visit and/or time-point where appropriate. Unscheduled or repeat assessments will not be included in summary tables, but will be included in listings.

Continuous variables will be summarized using descriptive statistics, including the number of observations (n), mean, standard deviation (SD), median, minimum, maximum and interquartile range (IQR). Categorical variables will be summarized using frequencies and percentages. Unless otherwise specified, percentages will be based on the total number of non-missing values.

Unless otherwise specified, all confidence intervals (CIs) will be 2-sided with a confidence level of 95%. No adjustments will be made for multiplicity.

All statistical analyses will be performed using SAS Version 9.4 or later for Windows.

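### Week 4, the step to 18 mg, keeps patients in clinic for 6 hours but schedules blood pressure and pulse only predose and at 1 hour, against 1, 3 and 6 hours at the two lower dose steps

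*Protocol*

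**What the plan says.** Protocol 3.1 requires a stay of at least 6 hours after the first double-blind dose on Day 1, and repeats this for Weeks 1 and 4: "At these visits, patients must again stay in the clinic at least 6 hours postdose to undergo safety, PRO, PK, and PD assessments". The synopsis says the same. The section leaves the timing of those assessments to the Schedule of Events.

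In the Schedule, the seated-to-standing row reads "predose pd: 1,3,6 (±15m") on Day 1 and at Week 1. The Week 4 cell has predose and 1 hour only, as at Weeks 8 and 12, where no dose step is planned. The separate averaged seated BP has no Week 4 entry. Footnote f names Screening, 6 hours on Day 1, and Week 1: "at predose and 6 hours postdose at the Week 1 Visit will be the average of 3 measurements obtained at 2-m intervals". Protocol 3.8.6.2 adds: "Other seated BP measurements and all pulse measurements may be single measurements". SAP Table 5b repeats this schedule.

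Week 4 is the step to 18 mg for patients who reached 12 mg at Week 1. For those who did not, Protocol 3.5.4.2 says "the patient will remain on 6 mg QD and will be re-assessed at Week 4 for titration to 12 mg QD". Patients cut to 3 mg in the first week may go back up, "with escalation to 6 mg QD considered at the Week 4 visit if they meet uptitration criteria" (Protocol 3.5.4.3).

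SAP Table 5a shows the same Week 4 entry under Amendment 3, "predose pd: 1h (±15m"). Under that amendment the full dose started after Week 1 (SAP Table 3), so Week 4 was not a dose step.

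**The concern.** The primary objective is safety and tolerability. Protocol 3.8.8.5 anticipates vasodilation and makes hypotension and tachycardia events of special interest. The plan follows BP for 6 hours after the first 6 mg and 12 mg doses, but for 1 hour after the first dose at the highest level.

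The same limit applies to two groups already held back: those who failed the Week 1 titration criteria and may take a first 12 mg dose at Week 4, and those re-challenged with a 6 mg dose they did not tolerate.

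Two things are at stake. A symptomless fall in BP after 1 hour has no scheduled reading to detect it. And SAP 8.1 analyses change from predose to each postdose time point, while SAP 5.1 says "Unscheduled or repeat assessments will not be included in summary tables, but will be included in listings" unless otherwise noted, so the 18 mg hemodynamic summaries will hold trough and 1-hour values only.

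A smaller point is that the uptitration criterion of seated systolic BP below 90 mmHg rests on a mean of three readings at Week 1 but may rest on one at Week 4.

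**Working it through.** The plan states no figure to reproduce here. The check compares visits in the Schedule and counts readings.

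**Scheduled postdose BP and pulse at each dose step** (Schedule of Events; SAP Table 5b)

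| Visit | First dose at | Seated-to-standing, postdose | Averaged seated BP at 6 h | Seated-to-standing times after 1 h |
|---|---|---|---|---|
| Day 1 | 6 mg | 1, 3, 6 h | yes | 2 |
| Week 1 | 12 mg | 1, 3, 6 h | yes | 2 |
| Week 4 | 18 mg | 1 h | no | 0 |

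The required stay is 6 h and the last scheduled Week 4 reading is at 1 h, so 6 − 1 = 5 h have no scheduled BP. At Day 1 and Week 1 the figure is 6 − 6 = 0 h. Across Weeks 4, 8 and 12 there are three postdose time points at 18 mg, all at 1 h.

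**Patients.** About 48 are planned under Amendment 4 and later, randomized 3:1, so 48 × 3/4 = 36 on active drug. This is an upper bound on those taking 18 mg, since some will not uptitrate.

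**What changed between amendments at Week 4** (SAP Table 5a against 5b). A next-day call was added, the PK sample moved from 2 h to end of visit, and a biomarker sample was added. The vital-sign cells are identical, although Week 4 had become a dose step.

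**Readings added by using the Week 1 entries at Week 4**

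- Week 1: predose 3 + 2, 1 h 2, 3 h 2, 6 h 3 + 2 = 14. If the averaged set also serves as the seated half of the orthostatic pair, 4 + 2 + 2 + 4 = 12.
- Week 4 now: predose 2, 1 h 2 = 4.
- Difference: 14 − 4 = 10, or 12 − 4 = 8, per patient.
- Over 48 patients: 480 or 384, if all attend Week 4 in clinic.

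**Precision of the titration reading.** With correlation r between the errors of readings at one visit, the error SD of one reading relative to the mean of three is √(3/(1 + 2r)). The documents give no r, so a range is assumed:

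| r | Ratio |
|---|---|
| 0 | 1.73 |
| 0.25 | 1.41 |
| 0.5 | 1.22 |

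Without a within-visit SD, this cannot be turned into a misclassification rate.

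**The case against.** The strongest reply is that lighter monitoring at Week 4 may be intended. Day 1 is first exposure and Week 1 doubles the dose, whereas 12 to 18 mg is a rise of 50% after about three weeks at 12 mg. Only patients who pass the BP, heart-rate and adverse-event criteria that day step up, and this includes those held back earlier. The Week 4 column was reworked, so the unchanged cells may be a choice. Protocol 3.5.3 is redacted and the Investigator's Brochure is not available here, so a rationale may exist. This stands: the absence of a visible reason is not evidence of an error. It does not supply a BP reading, though, and the absolute step is the same (12 − 6 = 6 mg; 18 − 12 = 6 mg).

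Second, the primary endpoint is treatment-emergent adverse events, collected whatever the BP timing. Symptomatic hypotension would be seen during the stay or reported at the next-day call. Unscheduled readings are possible, and SAP 7.4 counts them toward the orthostatic criteria. This also stands and narrows the concern to symptomless falls and the exploratory hemodynamic summaries.

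Third, averaging is allowed at Week 4 even though it is not required, and no effect on titration decisions has been shown. That is fair, and the averaging point is secondary.

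**Conclusion.** The concern holds as a gap in the Schedule that should be fixed. It is not a contradiction, because Section 3.1 defers to the Schedule. At the highest dose step there are no scheduled seated-to-standing readings after 1 hour, against two at each lower step, and about 5 of 6 clinic hours have no scheduled BP. The existing safeguards (observation in clinic, the next-day call, dose-reduction rules, special-interest event reporting and the trigger for data monitoring committee review) work mainly through symptoms and reported events. None ensures a reading after 1 hour.

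The clinical size cannot be stated, because the documents give no time of peak concentration or peak BP effect. The case rests on the plan's own choice to measure at 3 and 6 hours at the lower steps. The comparison of 18 mg with placebo patients randomized under Amendment 4 or later (PBO2) is not biased.

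**What to change.** In the Week 4 column of the Schedule of Events, use the Week 1 vital-sign entries: averaged seated BP and pulse predose and at 6 hours, and seated-to-standing BP and pulse predose and at 1, 3 and 6 hours, with the same 15-minute windows. In footnote f and Protocol 3.8.6.2, extend the average-of-three rule to predose and 6 hours at Week 4, so that it applies at both visits where the systolic criterion is used. Mirror the change in SAP Table 5b. Doses and titration thresholds stay as they are, and the SAP 8.1 analysis takes the added times without redesign.

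The text change is two Schedule cells, one footnote and one sentence, plus the matching SAP edits. In clinic it is 8 to 10 cuff readings per patient, at most 384 to 480 in all, with no extra visit and no longer stay. The amendment also needs IRB/IEC approval, eCRF changes and site retraining. The downsides are more staff time at one visit and two more exploratory time points. If the change comes after patients have passed Week 4, the 3- and 6-hour summaries there will cover only those treated later.
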